4.6.5 ECG

ECG results and corresponding changes from baseline will be summarized by visit for QT, RR, HR, QTcB, QTcF, PR and QRS and T- and U-wave morphology.

4.7 BIOMARKER ANALYSIS

Pharmacodynamic (PD) parameters (e.g., aPTT, FVIII activity) and other exploratory markers (FIX and FX antigens, PT/INR, D dimer) will be presented using summary statistics, including means, median, range, standard deviations, and coefficients of variation. In addition, individual patient plots will be provided. At the time of the interim analysis, only listings and patient plots will be performed.

4.8 MISSING DATA

On the electronic handheld device, it is not possible to leave questions unanswered or to enter partial data in one BMQ.

In the site data entry system, it is possible to leave the time (but not the date) of a treatment or a bleed blank because the caregiver might not be able to remember these in a reliable way.

In order to implement the 72 hour rule, it is assumed that the bleeds and treatments with missing time occurred at 12:00 a.m. If at a given day only the treatment time or the bleed time is partial and the other one complete, the partial time is assumed to be the same as the complete time. In case of multiple events per day, the last complete time is used.

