2.3.2.1 Treated Bleeds

A bleed is considered to be a “treated bleed” if it is directly followed (i.e., there is not an intervening bleed) by a hemophilia medication reported to be a “treatment for bleed”, irrespective of the time between the treatment and the preceding bleed. A bleed and the first treatment thereafter are considered to be pairs (i.e., one treatment belongs to one

bleed only), with the following exception: If multiple bleeds occur on the same calendar day, the subsequent treatment is considered to apply for each of these multiple bleeds.

Bleeds due to surgery/procedure are not included in the analysis. Only treatments that were recorded as “treatment for bleed” are included in the determination of a treated bleed. Note that a bleed can be treated with more than one treatment.

72-Hour Rule:

Two bleeds of the same type (e.g., “joint”, “muscle”, or “other”) and at the same anatomical location are considered to be one bleed if the second bleed occurs within 72 hours from the last treatment for the first bleed. The last treatment is defined as the last treatment before a new bleed occurs, either in the same or in a different location. This is consistent with the above definition that bleeds and treatments are considered to be pairs.

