2.4 DETERMINATION OF SAMPLE SIZE

The sample size for this study is based on feasibility and clinical considerations rather than statistical considerations, taking into account the number of pediatric patients with hemophilia A with inhibitors available for participation in this trial. Hence, at least 40 children younger than 12 years of age and up to approximately 80 patients with hemophilia A and FVIII inhibitors who are currently receiving treatment with bypassing agents will be enrolled in this study: approximately 60 patients in Cohort A with allowance of patients 12-17 years of age who weigh < 40 kg at the time of informed consent and with allowance for approximately 5 additional patients < 2 years of age in Cohort A - and approximately 10 patients each in Cohort B and Cohort C.

During the study, a re-assessment of the initially specified sample size based on enrolment consideration may be performed. This may result in an increase in sample size, if necessary, to expand the safety database.

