4. STATISTICAL METHODS

For continuous variables, means, medians, ranges, and standard deviations will be presented. For categorical variables, the number and percentage of patients within each category will be presented. For each variable (continuous or categorical), the number of available observations will be reported. No formal hypothesis testing will be performed as the study is entirely descriptive.

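### For site-entered records with a blank time, SAP 4.8 can place a bleed after its own injections or shift the 72-hour gap, so bleeds can be over- or under-counted

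*SAP*

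**What the plan says.** SAP 4.8 separates two routes of data entry. On the caregiver's device a time cannot be missing: "On the electronic handheld device, it is not possible to leave questions unanswered". At the site it can: "In the site data entry system, it is possible to leave the time (but not the date) of a treatment or a bleed blank". The SAP gives caregiver recall as the reason.

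Three imputation rules follow.

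- Default: "it is assumed that the bleeds and treatments with missing time occurred at 12:00 a.m".
- If only the bleed or only the treatment lacks a time on a given day, "the partial time is assumed to be the same as the complete time".
- A day with more than one event has its own rule: "In case of multiple events per day, the last complete time is used".

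These times feed two order-dependent steps in SAP 2.3.2.1. First, a treatment is paired with the bleed before it, "irrespective of the time between the treatment and the preceding bleed". Second, a bleed of the same type and location is merged into the previous one if it starts within 72 hours of that bleed's last treatment. SAP 2.3.2.2 applies the same window to untreated bleeds, counted from the bleed itself.

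Protocol 4.7.8 has a further rule that SAP 2.3.2.1 does not carry: an injection more than 72 hours after the preceding one marks a new bleed at that location. SAP 2.3.2.6 shows that site entry also contributes to the historical period from the non-interventional study.

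**The concern.** A bleed starts before it is treated, but nothing in SAP 4.8 enforces this. Taking the day's latest recorded time can put an untimed bleed after injections given for it. Because pairing has no time limit, those injections then belong to whatever bleed came before. A new same-site bleed can be merged away, or an older untreated bleed can become treated. There is also no rule for exact ties, although borrowing a time creates one by construction.

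The midnight default has a separate effect. Midnight is the edge of the day, so a blank injection time always lengthens the gap to the next bleed, and a blank bleed time always shortens the gap from the last injection.

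Bleed rate is the efficacy endpoint, and counts are expected to be low: Protocol 3.3.1 targets a trough at which the modelled median ABR is 0. At stake are the on-study bleed counts. The intra-patient comparison, which SAP 2.3.2.6 limits to all bleeds and treated bleeds, is exposed if blank times are more frequent in one period than in the other.

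**Working it through.** The plan states no figure that depends on these rules, so there is none to reproduce. The check applies SAP 4.8 and 2.3.2.1 literally to constructed records.

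**1. Order of bleed and injection.** In the first three cases the bleed truly starts at 07:00, its time is blank, and injections are recorded at 08:00 and 20:00. SAP 4.8 sets the bleed to 20:00, which is 20 − 8 = 12 h after its first injection. Two points are unspecified and were varied: whether the latest recorded time covers any event or only the opposite event type, and which event sorts first on a tie.

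| Case | True | Under SAP 4.8 |
|---|---|---|
| Isolated bleed | 1 treated | 1 if ties sort bleed first; 0 if treatment first |
| Same joint treated 10 days earlier | 2 bleeds | 1 under every reading and tie order |
| Untreated bleed elsewhere 10 days earlier | 1 treated | 2 with bleed-first ties; 1 with treatment-first ties, but the wrong bleed |
| Knee bleed blank (true 07:00), injection 09:00, other-site bleed 20:00 | 1 treated | 0 if any event counts; otherwise 1 with bleed-first ties, 0 with treatment-first |

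In the second case the 08:00 injection becomes the last treatment of the 10-day-old bleed. The new bleed at 20:00 is then 12 h from it and is absorbed.

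**2. Midnight default.** This applies only where no time is recorded that day. Let *t* and *b* be the true clock times (0–24 h) of the last injection and the next same-site bleed, and *g* the true gap.

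- Injection blank: imputed gap = *g* + *t*. Example: injection truly at 22:00, bleed 60 h later; 60 + 22 = 82 h, so one bleed becomes two.
- Bleed blank: imputed gap = *g* − *b*. Example: injection at 20:00, bleed 74 h later, which is 22:00 on the third day; 74 − 22 = 52 h, so two bleeds become one.

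For an injection on day T and a bleed on day T+3, *g* = 72 + (*b* − *t*), so the pair is truly within 72 h when *b* ≤ *t*. Assuming independent clock times uniform over the day (not from the documents), that is 50% of pairs.

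- Midnight, injection blank: imputed gap 72 + *b*, so essentially none merge; 50% wrong, all over-counted.
- Midnight, bleed blank: imputed gap 72 − *t*, so all merge; 50% wrong, all under-counted.
- Noon, injection blank: merge when *b* ≤ 12. Wrong if *t* < *b* ≤ 12 (1/8) or 12 < *b* ≤ *t* (1/8), so 25%, half each way. The bleed-blank case is symmetric.
- Both blank: midnight to midnight and noon to noon are each exactly 72 h, so all merge; 50% wrong one way under either rule.

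Simulation by true gap (200,000 draws per cell, same assumption) agrees. With the injection blank, 25% of decisions flip for gaps of 48–60 h and 75% for 60–72 h. With the bleed or both blank, 75% flip for 72–84 h and 25% for 84–96 h. No decisions flip in the other bands tested between 36 and 108 h.

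**3. Weight of one miscounted bleed.** Protocol 3.1 gives about 10 patients and about 6 months of efficacy follow-up in each of Cohorts B and C. One bleed moves a child's ABR by about 1/0.5 = 2 and the cohort rate by about 1/(10 × 0.5) = 0.2 per year.

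**The case against.** The strongest reply is that exposure is narrow. The handheld device cannot produce a blank time, entries are reviewed at visits and queried by the data manager and Medical Monitor (SAP 2.2), and the documents give no count of untimed records. The 50% figure needs the same type and location, a three-day calendar difference, exactly one blank time and no same-day time to borrow. The study also makes no formal inference: "No formal hypothesis testing will be performed as the study is entirely descriptive". All of this stands. It limits the point to what can happen and rules out any estimate of how often it does.

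A second reply is that SAP 4.4.1.1 refers to Protocol 4.7.8, whose late-injection rule would probably rescue the same-joint case. That is fair, but SAP 2.3.2.1, which sets out the counting rules, omits it. The rule would not help where the earlier bleed was untreated and elsewhere.

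A third reply is that the latest recorded time is sometimes right: a morning injection treats an old bleed, a new untimed bleed follows, and an evening injection treats that. This also stands. Using the earliest time errs there, so neither ordering is correct in every case.

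A reader might infer that midnight itself reverses the order. It does not: for same-day events it creates at worst a tie. The reversal comes from the rule for several events on a day.

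**Conclusion.** The point holds in a limited form. For site-entered records with a blank time, SAP 4.8 can miscount bleeds in either direction: by placing a bleed after its own injections, or by shifting the 72-hour gap by up to 24 h. The ordering cases follow from the stated rules, with their dependence on tie order shown above. The 50% and 25% figures rest on uniform clock times and apply only to the day T+3 pairs described.

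Three stronger readings are not supported.

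- That bleeds in this trial are miscounted: the share of blank times is not given, and an isolated bleed is still counted once if ties sort bleed first.
- That the errors cannot cancel, or that they favour emicizumab: they run both ways, and no net direction is shown.
- That all five bleed definitions are affected in the historical comparison: SAP 2.3.2.6 uses only two, and the comparison is distorted only if blank-time frequency differs between the periods.

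The change is still worth making, because a stated rule can give a wrong count and is cheap to correct.

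**What to change.** In SAP 4.8:

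1. Set a missing bleed time to the earliest complete time that day of a treatment recorded as given for a bleed.
2. State that a bleed sorts before its treatment on ties. Without this, rule 1 only creates a tie and can leave the injection with the previous bleed.
3. Where no same-day time exists and only one of the two times in the 72-hour comparison is blank, use noon instead of midnight. Where both are blank, the choice makes no difference.
4. Report the number of bleeds touched by each imputation rule, by study period.
5. Because rule 1 can give a new bleed an injection that treated an earlier one, show the bleed counts under both orderings for the affected records.

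Worked by hand, rules 1 and 2 restore the true counts in the last three ordering cases tabulated above. Some 72-hour error remains under any fixed imputed time. It would also help to state whether the late-injection rule of Protocol 4.7.8 applies within SAP 2.3.2.1. The cost is a few sentences, a small programming change and one short table.

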4.9 INTERIM ANALYSES

Interim data reviews by the JMC are described in Section [3.1](#). An additional interim analysis-for Study BH29992 will occur at the same time as the primary analysis of Study BH29884. This interim analysis-will be based on all available data from these pediatric patients and will be reported in an interim CSR. Other interim analyses might occur at any time in order to support health authority requests or submissions.

Appendix 1 Protocol Synopsis

TITLE:	A MULTICENTER, OPEN-LABEL, PHASE III CLINICAL TRIAL TO EVALUATE THE EFFICACY, SAFETY, AND PHARMACOKINETICS OF SUBCUTANEOUS ADMINISTRATION OF EMICIZUMAB IN HEMOPHILIA A PEDIATRIC PATIENTS WITH INHIBITORS
PROTOCOL NUMBER:	BH29992
VERSION NUMBER:	4
EUDRACT NUMBER:	2016-000073-21
IND NUMBER:	122954
TEST PRODUCT:	Emicizumab (RO5534262)
PHASE:	Phase III
INDICATION:	Hemophilia A
SPONSOR:	F. Hoffmann-La Roche Ltd and Chugai Pharmaceutical Co. Ltd.

Objectives and Endpoints

The objectives of the study are to investigate (with no formal hypothesis testing) the efficacy, safety, and pharmacokinetics of SC emicizumab administered at 1.5 mg/kg QW, 3 mg/kg Q2W, and 6 mg/kg Q4W in pediatric patients with hemophilia A and factor VIII (FVIII) inhibitors who are currently receiving treatment with bypassing agents. A total of approximately 80 patients are planned: approximately 60 patients in Cohort A (1.5 mg/kg QW) and approximately 10 patients each in Cohort B (3 mg/kg Q2W) and Cohort C (6 mg/kg Q4W). Patients younger than 12 years of age are planned for enrollment, with allowance of patients 12–17 years of age who weigh <40 kg at the time of informed consent to further evaluate dosing of emicizumab in patients <40 kg. Of note, enrollment in Cohort A may be left open exclusively for patients <2 years of age until approximately 5 such patients have been enrolled.

Efficacy Objective

The endpoints will be analyzed separately for the three cohorts: Cohort A (1.5 mg/kg QW), Cohort B (3 mg/kg Q2W), and Cohort C (6 mg/kg Q4W), and overall as appropriate.

The efficacy objectives for this study are as follows:

- To evaluate the clinical effect of prophylactic emicizumab on the number of bleeds over time (i.e., bleed rate) *
- To evaluate the efficacy in reducing the number of bleeds over time compared with the patient's historical bleed rate (intra-patient comparison, Cohort A only, as patients enrolled in Cohorts B and C will not have previously participated in the non-interventional study) *
- To characterize the efficacy of up-titration on an intra-patient level, based on the basis of the number of bleeds over time *
- To evaluate the health-related quality of life (HRQoL) of children 8–17 years of age according to Haemo-QoL-Short Form (SF) (completed by patients)

Appendix 1 Protocol Synopsis (Cont)

- To evaluate proxy-reported HRQoL and aspects of caregiver burden using the Adapted InhibQoL Including Aspects of Caregiver Burden questionnaire for all children (completed by caregivers)
- To assess the number of days missed from daycare/school and days hospitalized

* Analyses will be performed for: treated bleeds, all bleeds, treated spontaneous bleeds, treated joint bleeds, and treated target joint bleeds.

Safety Objective

The endpoints will be analyzed separately for the three cohorts: Cohort A (1.5 mg/kg QW), Cohort B (3 mg/kg Q2W), and Cohort C (6 mg/kg Q4W), and overall as appropriate.

The safety objective for this study is to evaluate the overall safety of emicizumab in pediatric patients with hemophilia A and inhibitors on the basis of the following endpoints:

- Incidence and severity of adverse events
- Incidence and severity of thromboembolic events
- Changes in physical examination findings and vital signs
- Incidence of laboratory abnormalities
- Incidence and severity of injection-site reactions
- Incidence of adverse events leading to drug discontinuation
- Incidence of severe hypersensitivity, anaphylaxis, and anaphylactoid events
- Incidence and severity of thrombotic microangiopathy
- Incidence and clinical significance of anti-emicizumab antibodies

Pharmacokinetic Objective

The endpoints will be analyzed separately for the three cohorts: Cohort A (1.5 mg/kg QW), Cohort B (3 mg/kg Q2W), and Cohort C (6 mg/kg Q4W).

The pharmacokinetic (PK) objective for this study is to characterize the exposure (C_{trough}) of emicizumab in patients receiving 1.5 mg/kg QW, 3 mg/kg Q2W, and 6 mg/kg Q4W prior to drug administration on Day 1 and at the following timepoints:

- Every week during Weeks 1–4 on emicizumab
- Every 2 weeks during Weeks 5–9 on emicizumab
- Every 4 weeks during Weeks 13–37 on emicizumab
- Every 8 weeks during Weeks 41–49 on emicizumab
- Every 12 weeks from Week 57 thereafter while continuing on emicizumab, until the end of the study
- Additional PK samples will be taken in patients who require up-titration (see schedule of assessments in the protocol)

Pharmacodynamic Biomarker Objective

The pharmacodynamic (PD) biomarker objective for this study is as follows:

- To assess potential PD biomarkers of emicizumab, including but not limited to aPTT and FVIII activity, at designated timepoints throughout the study.

Appendix 1 Protocol Synopsis (Cont)

Study Design

Description of Study

This *non-randomized*, multicenter, open-label, Phase III clinical study will enroll children with hemophilia A who have inhibitors against FVIII. Children with hemophilia A and documented historical FVIII inhibitor titer (≥ 5 BU) must currently be receiving treatment with bypassing agents. At least 40 patients younger than 12 years age and up to *approximately* 80 patients are planned for enrollment, with allowance of patients 12–17 years of age who weigh <40 kg at the time of informed consent. Patients will receive SC doses of emicizumab at 1.5 mg/kg QW (*Cohort A*) for a minimum of 52 weeks or until unacceptable toxicity, discontinuation from the study due to any cause, or other criteria set forth in the protocol, whichever occurs first. After 52 weeks of treatment, an individual patient who continues to derive clinical benefit may continue receiving prophylactic emicizumab as part of this study or a future separate emicizumab extension study.

Because of the uncertainty of the dosing regimen needed in patients <12 years of age or <40 kg to achieve similar exposure as in adults and adolescents, this study will *first* evaluate the appropriate dosing regimen in children by starting with the same *weekly* dosing regimen (1.5 mg/kg QW) being evaluated in the Phase III study (BH29884) in adult/adolescent patients with hemophilia A with inhibitors (see protocol for details). Emicizumab will be administered with a weekly dose of 3 mg/kg QW for the first 4 weeks followed by a maintenance dose of 1.5 mg/kg QW (*Cohort A*) for the remainder of the treatment period. During the 52-week treatment period, individual patients may have their dose up-titrated if they experience suboptimal bleeding control on emicizumab (see protocol).

In a first interim data review, the appropriateness of the initial dosing regimen will be evaluated (maintenance dose of 1.5 mg/kg QW) after the first 3–5 patients (≥ 2 to <12 years of age) have been dosed for a minimum of 12 weeks. A Joint Monitoring Committee (JMC; see protocol) will review all cumulative data (e.g., safety, efficacy, and pharmacokinetics) to provide recommendations on increasing the starting maintenance dose (if necessary) to target a similar plasma emicizumab trough concentration as the one being targeted in adolescents and adults (i.e., 45 µg/mL). All patients enrolled following the first interim data review will receive the starting maintenance dose selected by the JMC. Those patients enrolled prior to the first interim data review who had not had their dose up-titrated will remain on their current maintenance dose, unless they meet eligibility for up-titration based on protocol-defined criteria (see protocol).

In order to include and safely treat the youngest patients (birth to <2 years of age), this study will include a staggered approach to enrollment by age. Patients ≥ 2 to <12 years of age and patients 12–17 years of age who weigh <40 kg will enroll first. A second interim data review will occur once at least 10 patients between ≥ 2 and <12 years of age have been dosed for a minimum of 12 weeks, at which time all cumulative data (e.g., safety, efficacy, and pharmacokinetics) will be evaluated to provide recommendations for enrollment of children <2 years of age, as well as on any additional adaptations of the maintenance dose if necessary.

Furthermore, should patient recruitment be faster than anticipated, enrollment will be placed on a temporary hold following the first 20 patients until the JMC releases its recommendations on the appropriateness of the maintenance dose (*Cohort A*). After the JMC recommendations are released following both interim data reviews, the study will continue to enroll in *Cohort A* up to approximately 60 patients.

Once 1) the exposure at 1.5 mg/kg QW has been characterized in this pediatric population; 2) Cohort A is fully enrolled; and 3) review of data in adults and adolescents from two ongoing Phase III studies evaluating emicizumab at 3 mg/kg Q2W (BH30071) and 6 mg/kg Q4W (BO39182) identifies no safety concerns, this study will open two additional non-randomized cohorts to investigate Q2W and Q4W regimens in pediatric patients. Recruitment to Cohort B (3 mg/kg Q2W) and Cohort C (6 mg/kg Q4W) will occur in parallel with alternate cohort allocation via IxRS, for a total of approximately 10 patients per cohort.

Appendix 1 Protocol Synopsis (Cont)

Of note, enrollment to Cohorts B and C will be limited to patients 2–11 years of age. Emicizumab will be administered with a loading dose of 3 mg/kg QW for the first 4 weeks followed by a maintenance dose of 3 mg/kg Q2W (Cohort B) and 6mg/kg Q4W (Cohort C) for a minimum of 52 weeks, or until unacceptable toxicity, discontinuation from the study due to any cause, or other criteria set forth in the protocol, whichever occurs first (see protocol). During the 52-week treatment period, individual patients may have their dose up-titrated if they experience suboptimal bleeding control on emicizumab.

The entire study will enroll up to approximately 80 patients with allowance for additional patients < 2 years of age in Cohort A.

A patient who fulfills the inclusion and exclusion criteria should be enrolled at the Week 1 visit. Prophylactic use of bypassing agents should be discontinued *the day before* the first dose of emicizumab is given.

The primary analysis for all cohorts will be performed 52 weeks after all patients in the primary population of Cohort A have been enrolled or withdrawn prematurely, whichever occurs first. The primary population of Cohort A consists of all patients enrolled prior to the close of enrollment for patients ≥ 2 years of age (up to approximately 60 patients) and is used to define the timing of the primary analysis of Cohorts A, B, and C. If no patients < 2 years of age are included in the primary population of Cohort A, the primary analysis will still occur at the specified time; however, enrollment to Cohort A may be left open exclusively for patients < 2 years of age in order to enroll approximately 5 such patients. Note that these patients will be included in the primary analysis of Cohort A regardless of their follow-up time. Additionally, all available data from patients enrolled in Cohorts B and C (efficacy period approximately 6 months) will be included in the primary analysis of Cohort A.

During the study, caregivers will be asked to enter any individual bleeds, hemophilia-related medications, and emicizumab treatments that occur on an electronic, handheld device. Entries should be made at least weekly, *and also* at any time a bleed occurs or a hemophilia medication, *including* emicizumab, is administered. Detailed information about bleeds (type, location, date/time) will be captured. Detailed information about hemophilia medications (agent, dose, reason for administration, date/time) and emicizumab dosing (total volume, date/time) will also be captured. In addition, HRQoL using the Haemo-QoL-SF (completed by children 8 years of age and older), proxy-reported HRQoL and aspects of caregiver burden using Adapted InhibQoL (completed by caregivers of all children) and missed daycare/school will be collected on a separate electronic, handheld device during a patient's visit prior to emicizumab injection at Week 1 and every 12 weeks thereafter, as outlined in the schedule of assessments (see protocol). The number of days the child was hospitalized, if applicable, will be derived from data collected on eCRF.

Emicizumab is intended in this study for prophylactic use only (i.e., not to treat bleeds that have already occurred). Therefore, in this study all patients will continue to receive episodic treatment for breakthrough bleeds as needed. Breakthrough bleeds should preferably be treated with rFVIIa at the lowest expected dose to achieve hemostasis and captured as they occur on the electronic, handheld device. There is clinical experience in the ongoing Phase I/II clinical studies with the treatment of over 80 breakthrough bleeds in patients receiving emicizumab with either FVIII or bypassing agents. FVIII, aPCC, and rFVIIa do not interfere with emicizumab PK assessments, and no safety signals have been observed when breakthrough bleeds were treated with standard-of-care regimens during Phase I/II studies. However, in the ongoing Phase III Study BH29884 (adolescent and adult patients with hemophilia A with FVIII inhibitors), 3 events of TMA and 3 serious thromboembolic events were observed in patients who concomitantly used > 100 U/kg/day of aPCC on average for ≥ 24 hours for the treatment of breakthrough bleeds (see protocol). Therefore, it is recommended that breakthrough bleeds are treated with rFVIIa only, if possible, and that the use of aPCC or other bypassing agents should be avoided or limited (see protocol). Also, local and central laboratory assessments are required to monitor the risk for thromboembolic events or TMA as per the schedule of assessments (see protocol). Investigators will be asked to contact the Medical Monitor in the event of suspected lack or loss of efficacy of emicizumab in order to discuss potential laboratory

